Cover Page for ClinicalTrials.gov

Document

Study Protocol

Official study title

Clinical significance of real time PCR panel in children with acute gastrointestinal symptoms

Document Date

October 16, 2025

Clinical significance of real time PCR panel in children with acute gastrointestinal symptoms – RealCAGI

[name], [name], [name], [name], [name], [name], [name], [name], [name]

Abstract

Acute gastroenteritis is one of the most common reasons for pediatric emergency visits in both general and pediatric emergency departments. For most of the children rehydration is the only therapy needed. However, a range of bacterial pathogens may need accurate diagnosis and targeted antimicrobial therapy. Use of molecular multiplex testing has increased detection of pathogens in children with acute gastrointestinal symptoms. The PCR tests currently available enable rapid identification of gastrointestinal pathogens, with the test results often being available during the day sample was taken. However, it is unclear which of the patients are most likely to benefit from testing. Also, there is considerable uncertainty about the cost-effectiveness of the multiplex panels used to test for suspected infectious gastroenteritis in hospital and community settings. We have demonstrated that acute gastrointestinal symptoms are one of the most common diagnoses and a major cost in high-income population.

We hypothesize that real time multiplex PCR testing for gastrointestinal pathogens at pediatric emergency department setting could allow earlier initiation of appropriate antibiotics, reduce use of unnecessary antibiotics and improve identification of conditions in need for follow-up.

To assess the diagnostic performance of alternative sample types, we investigate the use of rectal swab and vomit in detecting gastrointestinal pathogens.

To estimate the usefulness of real time multiplex PCR testing, we will conduct investigator-driven academic clinical trial with randomized controlled study setting conducted at the Pediatric Emergency Department of Oulu University Hospital. For eligibility, children aged under 16 years arriving to pediatric emergency due to acute gastrointestinal symptoms will be assessed. After obtaining the written consent, fecal specimens will be collected by the nurses from the first stool after arriving to hospital. The pediatric nurses also collect rectal swab samples from each child. Vomit is also collected, if vomiting occurs.

The composite primary outcome consists of three outcomes which are evaluated using medical records: 1) correctly targeted antimicrobial treatment, 2) untargeted antimicrobial treatment and 3)

identification of conditions that require specific follow-up. Secondary outcomes, evaluated by medical records and electronic survey sent to families two weeks after the study visit, include: proportion of correctly targeted antimicrobial treatment, proportion of untargeted antimicrobial treatment, proportion of conditions in need for hospitalization or specific follow-up, time needed for clinician to receive the results of the samples, length of hospital stay, time to correct diagnosis, resolution of symptoms, laboratory and radiology costs, total costs, need for surgical consultation and proportion of patients needing surgical procedure, proportion of unscheduled revisits and proportion of correctly used hospital infection control measures.

In addition to the clinical trial conducted with fecal samples, we aim to assess the usability of rectal swab samples and vomit samples in identification of gastrointestinal pathogens.

1. BACKGROUND

Diarrheal diseases are the second leading infectious cause of mortality globally, after lower respiratory infections, among children younger than 5 years. Although childhood mortality due to diarrhea has declined substantially during previous decades, diarrhea is responsible for 500 000 deaths annually (GBD 2017). Acute gastroenteritis is one of the most common reasons for pediatric emergency visits in both general and pediatric emergency departments (Pöyry et al. 2021, Yoong et al. 2021). For most of the children rehydration is the only therapy needed. However, a range of bacterial pathogens may need accurate diagnosis and targeted antimicrobial therapy (Guarino et al. 2014).

In previous observational studies, use of molecular multiplex testing for all children who presented to the ED with acute gastroenteritis has increased detection of pathogens and decreased return visits (Pavia et al. 2023). However, it is unclear which of the patients most likely to benefit from testing. Also, there is considerable uncertainty about the cost-effectiveness of the multiplex panels used to test for suspected infectious gastroenteritis in hospital and community settings (Freeman et al. 2017).

Collection of fecal samples can be challenging and time consuming as children do not necessarily defecate during emergency visit. Finding the pathogens with recto-anal swab, that could be analyzed with real time multiplex PCR could significantly decrease the time to correct diagnosis. Rectal swabs have been reported to be reasonable option as sample collection method for real time PCR in children with or without diarrhea (Kabayiza et al. 2013) and in adults with norovirus infection (Siddler et al. 2014). Similarly, vomit samples have been reported eligible in identification of noroviral infection. (McHugh et al. 2018). The literature concerning usability of rectal swabs or vomit samples with multiplex PCR is however lacking.

We have demonstrated that acute gastrointestinal symptoms are one of the most common diagnoses and a major cost in high-income population (Pöyry et al. 2021).

2. RESEARCH HYPOTHESIS AND AIMS OF THE STUDY

Clinical significance of real time PCR panel for gastrointestinal pathogens

We hypothesize that real time multiplex PCR testing for gastrointestinal pathogens at pediatric emergency department setting could enhance initiation of appropriate antibiotics, decrease use of inappropriate antibiotics and increase identification of conditions in need for a particular follow-up or hospitalization.

The aim of the study is to evaluate the clinical significance of real time multiplex gastrointestinal PCR panel at pediatric emergency department.

Diagnostic study about alternative sample types for detecting gastrointestinal pathogens

We also hypothesize that rectal swab samples are a rapid and competent sample collection technique in identification of gastrointestinal pathogens with multiplex PCR in children with acute gastrointestinal symptoms.

Based on earlier literature, we hypothesize that rectal swab samples are rapid and competent sample collection technique in identification of gastrointestinal pathogens with multiplex PCR in children with acute gastrointestinal symptoms (Kabayiza et al. 2013). We also hypothesize that as in identification of norovirus, vomit samples could be utilized with multiplex PCR testing as well (McHugh et al. 2018). We aim to evaluate the sensitivity and specificity of rectal swab and vomit samples in relation to gold standard fecal samples.

3. METHODS

3.1 Clinical significance of real time PCR panel for gastrointestinal pathogens (RCT)

Study design and oversight

This is an investigator-driven academic clinical trial with randomized controlled study setting conducted at the Pediatric Emergency Department of Oulu University Hospital. The samples are processed in the NordLab clinical microbiology laboratory at Oulu University Hospital, where the diagnostic device is already in clinical use. The device has been as acquired by NordLab under national procurement legislation.

Study population and inclusion criteria

For eligibility, children aged under 16 years arriving in pediatric emergency due to acute gastrointestinal symptoms (vomiting and/ or diarrhea and/or abdominal pain and/or watery stool) will be assessed. Pediatric nurses in the ED screen children for eligibility upon arrival. Exclusion criteria are the need for cardiopulmonary resuscitation, immediate transfer to the intensive care unit, haematological disease or other severe immunosuppression, bloody diarrhea or a clinical suspicion of typhoid/paratyphoid fever. Otherwise, patients with comorbidities or prior antibiotic treatment are included. The multiplex PCR test is used only in children admitted to the study or those that meet the exclusion criteria.

Randomization

Before initiation of the study, a biostatistician who is not involved in the data collection creates a randomization list using a computer-generated random sequence of numbers, randomization being performed in permuted blocks of sizes varying randomly between 4 and 6. After obtaining written informed consent from each child's legal guardian and from children older than 6 years, the ED nurse opens the next opaque randomization envelope to assign the participant to either the intervention or control group (Figure 1).

[figure not shown]

Figure 1. Randomized, controlled trial study flow chart regarding the clinical benefit of active testing.

Sample Collection and Pathogen Detection

After obtaining the written consent, fecal specimens will be collected by the nurses from the first stool after arriving in hospital. We collect fecal samples from all the children in both groups (n =

526) following the IVD (in vitro diagnostic) protocols. Also, all fecal samples will be processed according to IVD protocols to ensure reliability of the results. The pediatric nurses also collect rectal swab samples from all children. If vomiting occurs, vomit samples are also collected.

Fecal specimens will be collected by the pediatric nurses from the first stool after arriving in the hospital. Sterile swab such as Copan Regular Flocked Swab 502CS01 will be used to insert the specimen into Cary-Blair medium (Copan FecalSwab) according to manufacturer's instructions. Rectal swab samples and vomit samples are collected using the same swab-kits. Swab is inserted approximately 2 cm into the rectum and rotated 3-4 times before removal. In case of vomiting, the swab is rotated in the gastric secretion. The specimens are then inserted into Cary-Blair medium solution, similarly to fecal samples.

Fecal samples will be tested with QIAstat-Dx gastrointestinal panel 2, which can detect 13 gastrointestinal bacterial species, 5 viral pathogens and 4 different parasitic species with results ready within 70 minutes (Table 1). Positive test result for *Clostridium Difficile* is complemented with an addendum "Clostridium Difficile is part of normal gut microbiota in children under 2 years of age". Following the IVD protocols, only fecal sample results are available to care taking physicians. Rectal swab and vomit results are only used for the methodological analysis (Figure 2). Threshold cycle (Ct) values for all samples will be recorded to estimate pathogen loads in different samples.

Study results are available to the clinicians mostly within a few hours from receiving the fecal sample in the intervention group. In the control group the results are delayed until 72 hours. By analyzing fecal samples in both groups, we ensure safety, transparency and enable a pathogen-specific impact analysis.

If the child is admitted to hospital and the test is considered necessary the following day, a new sample may be taken in addition to study samples.

Table 1. Pathogens detected by the QIAstat-Dx Gastrointestinal Panel 2

- Adenovirus F40/F41
- Astrovirus
- Norovirus (GI/GII)
- Rotavirus A
- Sapovirus (GI, GII, GIV, GV)
- *Campylobacter* (*C. jejuni*, *C. coli* and *C. upsaliensis*)
- *Clostridium difficile* (toxin A/B)
- Enterotoaggregative *Escherichia coli* (EAEC)
- Shigella/Enteroinvasive *Escherichia coli* (EIEC)
- Enteropathogenic *Escherichia coli* (EPEC)
- Enterotoxigenic *Escherichia coli* (ETEC) lt/st
- *Plesiomonas shigelloides*
- *Salmonella* spp.
- Shiga-like toxin-producing *Escherichia coli* (STEC) stx1/stx2* (including specific identification of *E. coli* O157 serogroup within STEC)
- *Vibrio vulnificus*
- *Vibrio parahaemolyticus*
- *Vibrio cholerae*
- *Yersinia enterocolitica*
- *Cryptosporidium*
- *Cyclospora cayetanensis*
- *Entamoeba histolytica*
- *Giardia lamblia*

*Shiga-like toxin-producing *E. coli* (STEC) genes (stx1 and stx2) are differentiated by QIAstat-Dx Gastrointestinal Panel 2

Follow-up

Primary outcome and most secondary outcomes will be assessed using medical record review. For selected secondary outcomes, we will follow the patients with electronic survey sent via e-mail two weeks after the study visit. The survey is established, and the answers are retained on the Red-CAP -platform. With the survey we estimate recovery of the child (duration of symptoms, return to day care or school). If the symptoms have not resolved by two weeks, an automated follow-up questionnaire will follow four weeks after the study visit.

Sample size calculation

With a composite primary outcome consisting of 1) use of correctly targeted antibiotic treatment, 2) avoiding incorrect antibiotic treatment and 3) identification of conditions in need for a precise follow-up, we regard a clinically significant difference if the proportion of children with a positive composite outcome is 20 % in the intervention group and 10 % in the control group. With an α error of 5% and a statistical power of 80 % and using 1:1 randomization, with an assumption of 20 % loss in retaining requested fecal samples, we need 263 children in intervention group and 263 controls, for a total of 526 children. We use all children with alternative sample types (rectal swab or vomit) for the diagnostic analysis.

Primary outcome

To assess the test's impact on clinical decision making, primary outcome composite includes three questions:

- 1) Was correctly targeted antimicrobial treatment started
- 2) Was untargeted antimicrobial treatment avoided
- 3) Was specific follow-up planned due to risk of complications (e.g. EHEC and hemolytic uremic syndrome)

within 72 hours from initial contact in Pediatric Emergency Room?

When any of these questions is answered YES, the composite variable is considered positive. Antimicrobial treatment is considered appropriate if a bacterial pathogen has been found and the patient meets criteria for severe gastroenteritis (aged under 1 year or immunocompromised or hospitalized due to gastroenteritis).

Secondary outcomes are proportion of correctly targeted antimicrobial treatment, proportion of conditions in need for hospitalization or specific follow-up, time needed for clinician to receive the results of the samples, length of hospital stay, time to correct diagnosis, resolution of symptoms, laboratory and radiology costs, total costs, need for surgical consultation and proportion of patients needing surgical procedure, proportion of unscheduled revisits, proportion of correctly isolated patients or correct use of personal protective equipment and the number of consultations for pediatric infectious diseases specialist.

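### Component 2 of the primary composite carries two different terms, and the protocol does not say whether its appropriateness rule governs it, so pathogen-directed treatment of a non-severe child can score as a success

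*Protocol*

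**What the plan says.** All references are to the protocol.

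- Section 3.1, Primary outcome: the composite has three questions, each judged within 72 hours of first contact, and one YES makes it positive. Question 1 is "Was correctly targeted antimicrobial treatment started". Question 2 is "Was untargeted antimicrobial treatment avoided". Question 3 asks whether specific follow-up was planned.
- Same paragraph, the only scoring rule: "Antimicrobial treatment is considered appropriate if a bacterial pathogen has been found and the patient meets criteria for severe gastroenteritis". Severe means "aged under 1 year or immunocompromised or hospitalized due to gastroenteritis".
- Section 3.1, Sample size calculation: component 2 is "2) avoiding incorrect antibiotic treatment".
- Abstract: the second component is listed as "2) untargeted antimicrobial treatment and 3", without saying that it is to be avoided.
- Section 2, hypothesis: the panel should "decrease use of inappropriate antibiotics".
- Section 3.1, Sample Collection and Pathogen Detection: intervention results mostly reach clinicians within a few hours. For controls, "In the control group the results are delayed until 72 hours". An admitted child may have a further sample the next day.

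Nothing in the text equates *untargeted*, *incorrect* and *inappropriate*, or ties the rule for *appropriate* to a particular question.

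**The concern.** In ordinary use the terms differ. Treatment is targeted if it is aimed at a pathogen that was found; under the protocol's rule it is appropriate only if the child also has severe disease. A drug aimed at a panel finding in a non-severe child is targeted but not appropriate. This is the overtreatment that an early panel result could prompt, and the hypothesis says that the panel should reduce inappropriate use.

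The outcome is scored from medical records, so whoever scores them must pick a reading. The choice does not cancel between the arms, because the two arms differ in when the panel result is seen.

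**Working it through.** **Test child.** Aged 1 year or more, not immunocompromised, not hospitalized for gastroenteritis; bacterial finding on the panel; drug aimed at it started within 72 hours; no specific follow-up planned. Question 3 is NO throughout.

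| The appropriateness rule governs | Q1 | Q2 | Composite |
|---|---|---|---|
| Q1 and Q2 | NO | NO | negative |
| Q1 only | NO | YES (nothing untargeted given) | positive |
| Neither | YES | YES | positive |
| Q2 only (read as *incorrect*) | YES | NO | positive |

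Only the first row agrees with the hypothesis. The term used for component 2 changes the composite only when Question 1 carries the severity condition (rows 1 and 2). When it does not, Question 1 itself counts treatment that fails the rule as a success.

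**Which arm.** The control hold (until 72 hours) covers the whole outcome window (72 hours). The next-day sample is for admitted children, and a child hospitalized for gastroenteritis is severe by the rule, so that route adds few test children. They therefore arise mainly in the intervention arm.

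**The plan's own figure.** Inputs from the Sample size paragraph: 20% against 10%, α 5% (taken as two-sided), power 80%, loss 20%.

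- n = [1.96·√(2·0.15·0.85) + 0.8416·√(0.2·0.8 + 0.1·0.9)]² / 0.10² = 198.97, so 199 per arm.
- With continuity correction: (198.97/4)·[1 + √(1 + 4/(198.97·0.10))]² = 218.5, so 219.
- 219 × 1.2 = 262.8, so 263 per arm, as stated. After the planned loss, 263 × 0.8 ≈ 210 can be evaluated.

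**Size.** Let f be the share of the intervention arm that are test children. The documents do not give f. Rescoring them from positive to negative lowers the intervention proportion by f, so each 1% is 1 point of the planned 10. For illustration, suppose that the planned 20% counts them as successes, with control at 10% and 210 per arm (normal approximation, no continuity correction):

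| f (assumed) | Intervention after rescoring | Power |
|---|---|---|
| 0% | 20% | 0.82 |
| 1% | 19% | 0.75 |
| 2% | 18% | 0.66 |
| 3% | 17% | 0.56 |
| 5% | 15% | 0.34 |
| 10% | 10% | no difference left |

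If the 20% leaves them out and they are scored as successes, f = 2% gives 22% (power 0.92) and f = 5% gives 25% (0.98). These figures presuppose that 10% and 20% are attainable, which depends on how untreated children are scored.

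**Untreated children.** Read literally, a child given no antimicrobial is YES on Question 2, so the composite is positive. If, say, 10% of an arm were treated (an assumption), at least 90% would be positive, which cannot fit planned rates of 10% and 20%.

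**The case against.** The strongest reply is that the authors meant the terms as synonyms and that the rule, which directly follows the three questions, governs all of them. Untargeted is then the complement of correctly targeted, and the test child is negative. That is a fair reading and may be the intended one, but the text does not state it, and the component is worded differently in the Sample size paragraph.

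A reader might go further and infer that the wording rewards panel-driven antibiotics and inflates the false-positive rate in favour of the panel. The documents do not support that. On the literal reading that makes the test child YES on Question 2, an untreated child is YES as well. Treating the child moves the composite from positive to positive: the outcome fails to penalise the treatment but gains nothing from it. To obtain an inflated error rate one must assume that untreated children are not YES, which abandons the reading that made the test child YES. One must also assume a value for f and a 10% base rate.

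A reader might also infer that the effect is confined to the intervention arm. The text restricts only the multiplex PCR. It does not exclude other stool testing in controls, so *mainly* is as far as it goes.

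**Conclusion.** The point holds as an inconsistency in the definition of the primary outcome that changes scores. The same child is positive or negative according to which term is used and which question the rule governs, and such children fall mainly in the intervention arm. As worded, the outcome can fail to count overtreatment that the hypothesis says the panel should reduce.

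The size is 1 point of the difference per 1% of the intervention arm, against 10 planned; the share itself is unknown. The conclusion rests on two assumptions: that *untargeted* has its ordinary meaning, and that the authors have not equated the terms elsewhere. It should be settled before any outcome is scored, because it concerns the primary outcome and does not cancel between the arms.

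**What to change.** 1. Use one term for component 2 in the Abstract and in the Sample size and Primary outcome paragraphs, and the same term for the matching secondary outcome in the Abstract.
2. State that the protocol's appropriateness rule governs both Question 1 and Question 2, and that pathogen-directed treatment that fails the rule is NO on both.
3. In the same edit, state how a child given no antimicrobial is scored on Question 2, so that the definition can yield rates near the planned 10% and 20%. Aligning the terms alone would leave every untreated child at YES.
4. State whether treatment of a detected parasite (the panel covers four), or of an infection outside the gut, falls under the rule, which at present requires a bacterial pathogen and severe gastroenteritis.

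The content of the severity rule stays with the sponsor's clinicians; only the scoring has to follow it. The cost is a change of protocol wording before scoring begins. The downside is that the result may look slightly less favourable to the panel.

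### Primary component 3 scores follow-up that was planned, not follow-up that was needed, and follow-up prompted by a study result can count mainly in the intervention arm

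*Protocol*

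**What the plan says.** The protocol describes component 3 in two ways.

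- **By need.** The abstract has "identification of conditions that require specific follow-up". Section 2 hypothesises that testing will "increase identification of conditions in need for a particular follow-up or hospitalization". The sample size calculation in 3.1 has "identification of conditions in need for a precise follow-up".
- **By action.** The question that is actually scored, in 3.1 under Primary outcome, is "Was specific follow-up planned due to risk of complications", with EHEC and hemolytic uremic syndrome given in brackets as the example. It is assessed over the first 72 hours after first contact.

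The combination rule is "When any of these questions is answered YES, the composite variable is considered positive", so component 3 alone can make a child a success. The same paragraph sets a standard for treatment: "Antimicrobial treatment is considered appropriate if a bacterial pathogen has been found and the patient meets criteria for severe gastroenteritis", with severity criteria listed after it. It sets no matching standard for follow-up.

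Under Sample Collection and Pathogen Detection, stool is tested by the panel in both arms. Clinicians mostly see the result within a few hours in the intervention arm; in the control arm it is held back until 72 hours. An admitted child may have a further sample the next day if this is thought necessary. The primary outcome is assessed by medical record review.

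**The concern.** A child whose follow-up was planned after a panel result scores YES whether or not the child had a condition that called for it. The wording cannot tell a correctly identified risk from precaution after a finding of no consequence.

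The timing makes this matter for the comparison between arms. If unneeded follow-up arose equally in both arms, it would mainly add noise. Here the trigger, a visible study result inside the outcome window, is largely confined to one arm by design. True benefit and overuse would both appear as extra YES answers in the intervention arm. A positive primary result could then not be read as better identification of children in need, which is what the hypothesis claims.

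**Working it through.** **1. Wording side by side.**

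| Place in Protocol | What makes the component positive |
|---|---|
| Abstract | a condition requiring follow-up is identified |
| Section 2, hypothesis | a condition in need of follow-up (or hospitalization) is identified |
| 3.1 Sample size calculation | a condition in need of follow-up is identified |
| 3.1 Primary outcome (scored) | specific follow-up is planned, for complication risk |

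Three statements are need-based, and the one that decides the outcome is action-based. Its only filters are that the follow-up be specific and that complication risk be the reason.

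**2. Timing.** The outcome window is 72 hours from first contact. The protocol does not say when the 72-hour delay for controls starts. From first contact, the result arrives as the window closes; from sample receipt, it arrives later still. Either way a control child's study result can hardly prompt follow-up that counts. The exceptions are a repeat sample in an admitted child and follow-up planned on clinical grounds.

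**3. The plan's own figure.** With 20% v 10%, two-sided 5% (sidedness is not stated) and 80% power:

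- n₀ = [1.96·√(2·0.15·0.85) + 0.8416·√(0.2·0.8 + 0.1·0.9)]² / 0.1² = 199 per arm
- with continuity correction: n = (n₀/4)·[1 + √(1 + 4/(n₀·0.1))]² = 219
- 219 × 1.2 = 262.8, giving the stated 263

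With 20% of stool samples lost, 263 × 0.8 = 210 evaluable children per arm. The target difference is 10 points.

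**4. Illustration (assumed rates).** The documents give no rate of unneeded follow-up. Let x be the share of otherwise-negative intervention children who receive it, with 10% success from all other causes in both arms and no true benefit. Then p₁ = 0.10 + 0.90·x, p₀ = 0.10, and the shift is 0.90·x. The chance of a significant result favouring the intervention is Φ[(p₁ − p₀ − 1.96·SE₀)/SE₁], where SE₀ is the pooled and SE₁ the unpooled standard error, at 210 per arm. Its nominal value is 2.5%.

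| x | p₁ | shift | chance of a significant result |
|---|---|---|---|
| 2% | 11.8% | 1.8 points | 8.6% |
| 5% | 14.5% | 4.5 points | 29% |
| 10% | 19.0% | 9.0 points | 75% |

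**5. Two sensitivities.**

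- *Leakage.* If controls receive unneeded follow-up at one fifth of x, then p₀ = 0.10 + 0.90·0.2·x. At x = 5% this gives 14.5% v 10.9% and a chance of 20%; at x = 10% it gives 19.0% v 11.8% and 53%.
- *Component 2.* If every child not given untargeted antimicrobials scores YES, background success might be a = 80% to 95%, again an assumption. The shift is (1 − a)·x. At x = 5% to 10% it runs from 0.05 × 0.05 = 0.25 points to 0.20 × 0.10 = 2 points, and the chance is 3% to 8%.

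**The case against.** The strongest reply is that the composite is introduced as a measure of the test's effect on clinical decisions. Planning follow-up is such a decision, and early results are the intervention, so more follow-up in that arm is the effect under study. This is right as far as it goes: asymmetry alone is not bias. It becomes bias only to the extent that the follow-up was not needed. But the hypothesis and the sample size section claim identification of need, and the scored question does not measure that.

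A reader might infer three stronger things that the documents do not support.

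- *That any follow-up scores.* It does not. It must be specific and due to complication risk, with EHEC and hemolytic uremic syndrome as the example, so routine rechecks do not qualify. This filter tests the recorded motive rather than need, so it narrows the gap without closing it.
- *That the protocol itself shows overuse after incidental positives.* The one non-causal positive it acknowledges carries the addendum "Clostridium Difficile is part of normal gut microbiota in children under 2 years of age". That is a warning to the clinician, and nothing links this result to complication-driven follow-up.
- *That a known share of the planned effect is artefact.* No rate is given, and the result depends on leakage and on how component 2 is scored.

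It can also be said that a list of qualifying conditions belongs in the statistical analysis plan, which is not shown, and that a need-based proportion already stands among the secondary outcomes. Both are fair. However, the protocol itself fixes the scored question, and a secondary outcome does not change what the primary one counts.

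**Conclusion.** The point holds as a mismatch between the construct and its scoring, made consequential by the result timing. The mismatch, the missing need criterion and the alignment of withholding with the outcome window are all in the text.

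The size of the bias is not known. Under the protocol's 10% control rate the illustrative shift is 1.8 to 9 points for x between 2% and 10%, against a target of 10. If most untreated children already score YES on component 2, it is 2 points or less and of little consequence. That second reading sits badly with the planned 10% and 20% rates, but the wording does not exclude it. These figures assume no true benefit, 210 evaluable children per arm and, apart from the leakage case, no unneeded follow-up in controls. They show what the definition would allow, not what will happen. The change is worth making because the mismatch is certain and the remedy is cheap.

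**What to change.** Reconcile the scored question with the need-based descriptions:

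- Score component 3 YES only when specific follow-up was planned within the 72-hour window **and** the child has a condition on a list fixed before outcome review. Which conditions are listed is for the investigators to decide.
- Judge the condition from the stool panel, which is run in both arms. Where there is no stool result, use other records under one rule for both arms. Assess without knowledge of allocation where possible.
- Report planned follow-up without a listed condition, by arm, as a separate overuse outcome.

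The cost is a change of wording and a list agreed in advance, with no new visits or samples. Three limits remain. Fewer component 3 events will count. The 20% of children expected to lack a stool sample depend on the records-based rule, and what the records contain may itself reflect whether a result was seen. An incidental detection of a listed pathogen would still score YES.
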